13.7.4 Adverse Events of Special Interest Reporting

Beginning from the time of first study drug infusion and ending at the time of the Day 197 visit, the Day 372 visit (for subjects participating in the OLE period), the ET Visit, or the end of the Extended Follow-Up period (if applicable), any new AESI (or new information related to a previously reported AESI) must be recorded in the Adverse Event eCRF and designated as an “adverse event of special interest.”

For subjects participating in the OLE period, AESI will be assessed and recorded in the CRF of the AK002-014 treatment period database up until the start of the first open-label infusion during the Day 176 visit and recorded in the CRF of the AK002-014 OLE period database beginning from the start of the first open-label infusion during the Day 176 visit.

An AESI that also qualifies as a SAE (per Section 13.2) must also be reported as a SAE in accordance with Section 13.7.2. AESI that are also SAE must be recorded in the Adverse Event eCRF and designated as both “serious” and an “adverse event of special interest.” These will be reported on the Sponsor-provided SAE forms and should be reported to the Sponsor within 24 hours of site awareness.

13.9 Independent Data Monitoring Committee

An independent Data Monitoring Committee (iDMC) has been convened for this study. The iDMC will meet at established intervals throughout the study and will also convene as necessitated by data and/or safety reviews.

13.10 Study Withdrawal Criteria

Participation of a subject will be discontinued in the event that:

- Occurrence of an exclusion criterion, which is clinically relevant and affects the subject's safety, if discontinuation is considered necessary by the Investigator and/or Sponsor.
- Rebounding of eosinophil counts to $>1500/\mu\text{L}$ in subjects who entered the study with eosinophil levels $>1500/\mu\text{L}$ and whose eosinophil counts were initially suppressed after study drug will be withdrawn from the study at the instruction of the Safety Monitor.
- Serum transaminases (ALT and/or AST) $>3 \times \text{ULN}$ and total bilirubin $>2 \times \text{ULN}$ (confirmed by subsequent repeat testing) without an alternative explanation.
- Elevation of ALT or AST $>3 \times \text{ULN}$ (confirmed by repeat testing) with the appearance or worsening of symptoms that the Investigator believes to be potentially related to hepatic inflammation such as fatigue, nausea, vomiting, right upper quadrant pain or tenderness, fever, or rash.

13.11 Study Stopping Rules

The study may be discontinued prematurely in the event of any of the following:

- A life-threatening AE that is possibly or probably related to treatment.
- A fatal AE that is possibly or probably related to treatment.
- New information leading to an unfavorable risk-benefit judgment of the study drug.
- Sponsor's decision that continuation of the trial is unjustifiable for medical or ethical reasons.
- Discontinuation of development of the Sponsor's study drug.

Health Authorities and IRB will be informed about the discontinuation of the trial in accordance with applicable regulations. The trial may be terminated or suspended on request of Health Authorities or Sponsor.

14. Discontinuation and Replacement of Subjects

14.1 Definition of Study Completion

A subject who does not participate in the OLE period and who completes visits through the Day 197 visit or, if applicable, the last Extended Follow-Up visit after completing Day 197, will be recorded as having completed the double-blind portion of the study.

A subject who completes visits through the Day 169 visit and participates in the OLE period of the study will be recorded as having completed the double-blind portion of the study.

A subject who participates in the OLE period of the study and completes visits through the Day 372 visit or, if applicable, the last Extended Follow-Up visit after completing Day 372, will be recorded as having completed the OLE portion of the study.

14.2 Early Discontinuation of Study Drug

A subject may be discontinued from study treatment at any time if the subject, the Investigator, or the Sponsor believes that it is not in the subject's best interest to continue. The following is a list of possible reasons for study treatment discontinuation:

- Subject withdraws consent.
- Adverse event that in the opinion of the Investigator results in study treatment discontinuation being in the best interest of the subject.
- Protocol violation requiring discontinuation of study treatment.
- Participation in any other study during the duration of this study.
- Use of a non-permitted concomitant drug without prior approval from the Medical Monitor.
- Loss of ability to freely provide consent through imprisonment or involuntary incarceration or treatment of either a psychiatric or physical (e.g., infectious disease) illness.

If a subject is withdrawn from treatment due to an AE, the subject will be followed and treated by the Investigator until the abnormal parameter or symptom has resolved or stabilized.

All subjects who discontinue study drug treatment should be encouraged to continue on study and complete assessments and procedures according to the follow-up period in [Table 1](#), if possible (including follow-up EGD).

Reasonable attempts will be made by the Investigator to provide reasons for subject withdrawals. The reason for the subject's withdrawal from the study, or all attempts to acquire such, will be specified in the source documents.

Enrolled subjects who discontinue the study early will not be replaced.

15. Statistical Methods

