----------------------------------	---

Study Design cont.	
 • Subjects who are not eligible for (or who choose not to participate in) the OLE period will be followed for approximately 8 weeks after the last dose per the Schedule of Events (Table 1), including the Day 169 visit (4 weeks after the last dose) and the Day 197 visit (8 weeks after the last dose). • If absolute lymphocyte and/or eosinophil counts have not recovered by Day 197 (or Day 372 for subjects in the OLE period), subjects will return approximately every 28 days for extended follow-up until counts recover. • Total study duration is approximately 33–36 weeks (or 58–61 weeks for subjects participating in the OLE period), though the study duration could be extended for monitoring absolute lymphocyte and/or eosinophil counts (as described above).
Primary Efficacy Objective	
To evaluate the efficacy of AK002 in adult and adolescent subjects with active EoE when compared to placebo, efficacy endpoints will be co-primary:
 
 1) The proportion of subjects who achieve a peak esophageal intraepithelial count of ≤ 6 eosinophils/hpf at Week 24. 2) Mean change in Dysphagia Symptom Questionnaire (DSQ) score from Baseline to Weeks 23–24.
Secondary Objectives	
To further evaluate the efficacy of AK002 in adult and adolescent subjects with active EoE when compared to placebo as measured by:
 
 1) Percent change in peak esophageal intraepithelial eosinophil count at Week 24. 2) Proportion of subjects achieving peak esophageal intraepithelial eosinophil count of ≤ 1 eosinophil/hpf at Week 24. 3) Proportion of subjects achieving peak esophageal intraepithelial eosinophil count of < 15 eosinophils/hpf at Week 24. 4) Proportion of treatment responders when a responder is a subject achieving $> 30\%$ reduction in symptoms (DSQ) at Weeks 23–24 and achieving a peak intraepithelial eosinophil count of ≤ 6 eosinophils/hpf at Week 24. 5) Proportion of subjects with $> 50\%$ reduction in DSQ score from Baseline to Weeks 23–24. 6) Percent change in DSQ score from Baseline to Weeks 23–24. 7) Change in biweekly mean DSQ over time. 8) Change in EoE Reference Score for Endoscopic Abnormalities from Baseline to Week 24.

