
Duration of Subject Participation
	
The total study duration for each subject will be either 33–36 weeks or 58-61 weeks, including and depending on:
 
 • Screening period of 14–60 days (or a maximum of 35 days after the Screening EGD, whichever is shorter) prior to study drug administration.

Duration of Subject Participation cont.
	
 • Treatment period of 24 weeks (± 3 days) beginning the day of the first dose and ending 4 weeks after the last dose. • Optional Open-Label Extended Dosing Period of 28 weeks (± 3 days), or Follow-up period of 4 weeks (± 3 days). 
Regardless of whether a subject participates in the OLE period or not, all subjects will be followed for 8 weeks after the last dose of study drug. If lymphocyte or eosinophil counts have not recovered by Day 197 or Day 372 for subjects participating in the OLE period, subjects will return every 28 days for extended follow-up until counts have recovered.

Safety Evaluations
	
Safety and tolerability will be assessed throughout the study by monitoring and evaluating AE, including any complications resulting from the intravenous infusion. All TEAE will be collected from the start of study drug administration through Day 197 (± 3 days) or Day 372 (for subjects participating in the OLE period) or Early Termination.
 
Severity of AE will be assessed using the National Cancer Institute Common Terminology Criteria for Adverse Events (Version 5.0 or most current version). All AE will be assigned a severity grade and will be assessed for clinical significance and relationship to study drug.
 
Additional safety evaluations include clinical laboratory tests, including anti-drug antibody to AK002, complete blood counts, chemistries, and urinalyses as well as physical exams and vital signs measurements.
 
The Medical Monitor will review blinded safety data throughout the study. The safety monitor will review blinded safety data and escalate to the Medical Monitor as appropriate.
 
An independent Data Monitoring Committee (iDMC) has been convened and will meet at regularly scheduled intervals in accordance with the iDMC charter.
 
During the period of extended follow-up, data collection will be limited to hematology, serious adverse events, and adverse events of special interest.

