- A 14 to 60-day (or a maximum of 35 days after the Screening EGD, whichever is shorter) screening period with baseline evaluations for eligibility, including baseline disease activity (by daily PRO questionnaire) and esophago-gastro-duodenoscopy (EGD) with biopsy.
- Prior to the first dose of study drug (12–24 hours prior to the infusion), subjects will be premedicated with oral prednisone (40 mg if body weight is < 40 kg, 60 mg if body weight is ≥ 40 kg and < 60 kg, or 80 mg if body weight is ≥ 60 kg).
- Eligible subjects will receive 6 doses of AK002 (or placebo) by IV infusion on Days 1, 29 (± 3), 57 (± 3), 85 (± 3), 113 (± 3), and 141 (± 3). Subjects will self-administer prednisone 12–24 hours prior to the start of the first infusion only.
- Subjects will remain at the site for at least 1 hour of observation after each dose. In the event of an IRR, the subject may require prolonged observation (> 1 hour or until the symptoms resolve), as per Investigator discretion. Subjects will also be instructed to immediately contact the study doctor if any reactions occur after discharge.
- A repeat EGD with biopsy will be performed on Day 169 (± 3) or 28 (± 3) days after last dose if subject is terminated early between Day 29 and Day 169 study visits.
- After completion of the Day 169 visit, the Investigator will evaluate whether the subject is eligible for the OLE period.
- Subjects who are eligible and choose to participate in the OLE period will begin following the OLE Schedule of Events (Table 5) on Day 176 (± 3). The OLE period includes 6 doses of open-label AK002 administered on Days 176 (± 3), 204 (± 3), 232 (± 3), 260 (± 3), 288 (± 3), and 316 (± 3) and post-treatment follow-up visits on Day 344 (± 7) and Day 372 (± 7).

- Subjects who are not eligible for (or who choose not to participate in) the OLE period will be followed for approximately 8 weeks after the last dose per the Schedule of Events ([Table 1](#)). The Follow-Up Period includes the Day 169 (± 7) visit (4 weeks after the last dose) and the Day 197 (± 7) visit (8 weeks after the last dose).
- If absolute lymphocyte and/or eosinophil counts have not recovered by the Day 197 visit (or the Day 372 visit for subjects participating in the OLE period), subjects will return approximately every 28 days for extended follow-up until counts have recovered.

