- C. Any subject requiring a therapeutic EGD (defined as dilatation or other intervention for a narrowing or stricture) that may impact subsequent assessment of the DSQ during the first qualifying EGD at the end of the screening period or at any point during the study through Study Week 24.
- D. Discontinuation of Investigational Medical Product
  - 1) Discontinuation of study agent due to
    - a) Infusion-related reaction
    - b) Subject withdrawal
    - c) Meeting study withdrawal criteria (Protocol Section 13.10)

Per protocol, subjects are required to remain on stable doses of either PPI or corticosteroids ( $\leq 10$  mg of prednisone equivalent per day) throughout the course of the study if they are on a stable dose during the screening period. Because of the potential impact of corticosteroids and PPI on both histologic assessment of tissue eosinophil levels as well as patient-reported GI symptoms, subjects must meet the entry requirements for both histology and symptom burden (DSQ) if they are on any of these medications at screening, and therefore, must remain on a stable dose throughout the study in order to meaningfully interpret any change from baseline during the evaluation phase. Conversely, subjects starting these medications due to unforeseen medical necessity following the screening period and remaining on them through a time point sufficiently close to the evaluation period to potentially impact assessment of symptoms and/or histologic assessments will be considered as ICE. For PPI and corticosteroids ( $\leq 10$  mg/day of prednisone or equivalent), a conservative washout period is estimated at 2 weeks, and therefore, continuation of a new course of therapy beyond Week 21 could be considered as a potential ICE.

Sodium cromolyn is a mast cell stabilizer and could potentially impact reported symptoms in a similar way to one of the mechanisms of action of AK002. As such, discontinuation of a previously stable dose of sodium cromolyn after the screening period and before the end of Week 24 could be considered as a potential ICE. Likewise, the initiation or increase in the dose

of sodium cromolyn following the screening period and continuing to at least Study Week 22 (within 1 week of efficacy assessment at Weeks 23 and 24) could be considered as a potential ICE. It is estimated that 1 week would be a sufficient washout period for the effects of sodium cromolyn.

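### For subjects who stop study drug but stay in the study, the follow-up period has conflicting time anchors, and one of them ends the DSQ diary before Weeks 23–24 if the last dose was dose 1, 2, 3 or 4

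*Protocol*

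**What the plan says.** Protocol 14.2 deals with subjects who stop drug but do not leave the study: "All subjects who discontinue study drug treatment should be encouraged to continue on study and complete assessments and procedures according to the follow-up period" of Table 1, if possible and with the follow-up EGD. It does not tell them to keep the remaining scheduled visits. Subjects on rescue therapy, by contrast, are told in Protocol 8.1 and 10.4 to keep all visits and assessments in Table 1.

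No Table 1 column is headed follow-up period, apart from extended follow-up, so the reader has to look for the definition elsewhere. Three versions are found:

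- **Calendar days.** The Table 1 columns are Day 169 and Day 197. Protocol 14.1 defines completion the same way: "A subject who does not participate in the OLE period and who completes visits through the Day 197 visit".
- **Time since last dose.** The synopsis (Study Design) describes follow-up as "including the Day 169 visit (4 weeks after the last dose) and the Day 197 visit (8 weeks after the last dose"), and Protocol 5.1 repeats this. The synopsis section on duration of participation describes the treatment period as "beginning the day of the first dose and ending 4 weeks after the last dose" and adds that "all subjects will be followed for 8 weeks after the last dose of study drug".
- **Twelve weeks.** SAP 4.2.5 attributes to the protocol a 12-week follow-up for subjects withdrawn from treatment after starting a prohibited medication.

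Table 1 has the DSQ completed daily until End of Study or early termination.

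**The concern.** Both co-primary endpoints sit at fixed times counted from Day 1: histology at Week 24 and DSQ at Weeks 23–24. Section 14.2 applies mainly to subjects who did not receive all six doses, and these are the subjects for whom the calendar and last-dose anchors part. A site that counts from the last dose could do the End of Study visit, and so close the diary, well before Week 23. It could also take the follow-up biopsy early. A site that uses calendar days would do neither.

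For a subject with no intercurrent event (ICE), the site's reading then decides whether the DSQ endpoint is observed or imputed. SAP 5.4.2 would impute it by MCMC within the subject's own arm. SAP 6.11.5 starts from that imputed data set and resets only post-ICE values, so as written neither DSQ sensitivity analysis would test this imputed value.

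An early biopsy could enter as the Week 24 result through its visit label. It could also enter through SAP 5.4.1, which fills a missing Week 24 count from an earlier post-baseline unscheduled visit. SAP 5.2 gives no analysis window for biopsy or EREFS that would settle this. (The title of SAP Table 3 is blacked out, but its visits include every dosing day, so it is not an EGD table.)

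**Working it through.** **Inputs.** Dosing days 1, 29, 57, 85, 113 and 141 (Protocol 4.5.3). Follow-up visits 4 and 8 weeks after the last dose, that is +28 and +56 days (synopsis, Protocol 5.1). Study weeks are 7 days counted from Day 1 (SAP Table 2).

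**Endpoint window.** Week 23 opens on Day 22 × 7 + 1 = 155 and Week 24 closes on Day 24 × 7 = 168.

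**The plan's own figures.** 141 + 28 = 169 and 141 + 56 = 197. The two protocol anchors therefore agree for a Day 141 last dose. The SAP's 12 weeks, if counted from the last dose (an assumption, since the SAP does not say), gives 141 + 84 = 225 and agrees with neither.

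**Earlier stops under the last-dose anchor.** Biopsy day = last dose + 28, and its lead = 169 − biopsy day. Diary end = last dose + 56, and its gap = 155 − diary end.

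| Last dose | Biopsy day | Days before Day 169 | Diary ends | Days before Day 155 | DSQ window |
|---|---|---|---|---|---|
| 1 (Day 1) | 29 | 140 | 57 | 98 | none |
| 2 (Day 29) | 57 | 112 | 85 | 70 | none |
| 3 (Day 57) | 85 | 84 | 113 | 42 | none |
| 4 (Day 85) | 113 | 56 | 141 | 14 | none |
| 5 (Day 113) | 141 | 28 | 169 | – | all 14 days |
| 6 (Day 141) | 169 | 0 | 197 | – | all 14 days |

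These are nominal days; accepted visit windows move them by some days. Under the calendar anchor nothing shifts for anyone.

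**With 12 weeks (+84 days).** The diary ends on Day 85, 113 or 141 after dose 1, 2 or 3, which is 70, 42 or 14 days before Day 155. After dose 4 it ends on Day 169 and the window is covered.

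**Which stops matter for the planned analyses.** SAP Appendix 2 item D counts stopping study agent as an ICE for three reasons: infusion-related reaction, subject withdrawal, or meeting the criteria of Protocol 13.10. After an ICE, DSQ values are set to missing and binary outcomes count as non-response (SAP 4.2.5, 5.4.2), so later diary data would not be used in any case. Protocol 14.2 allows other reasons, such as an adverse event judged by the investigator to warrant stopping, or a protocol violation. A subject who stops for a non-infusion adverse event and stays on study is not clearly in item D. The general list in SAP 4.2.4 names premature discontinuation from the study, not from drug. The anchor affects the primary analyses for this group.

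**The case against.** The calendar reading has good support. Section 14.2 points to Table 1, whose columns are calendar days. The wording that counts from the last dose appears where Protocol 5.1 discusses subjects not entering the open-label period, a choice made after Day 169; for anyone dosed on Day 141 it is plain arithmetic. The explicit rule of an EGD 28 days after the last dose is written for early termination (Table 1 notes 14 and 32, Protocol 12.13). All of this stands, so the early schedule is a possible reading and not the required one. It does not remove the conflict, because the synopsis follows all subjects for 8 weeks after the last dose without exception and no passage says which anchor governs.

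Three stronger inferences are tempting, and the documents do not support them.

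- **That the plan's 14% sizes the problem.** It is a dropout rate. No rate is given for subjects who stop drug and stay, so no count per arm or precision loss can be derived.
- **That a subject could complete the study at about Day 85 with no ICE.** This needs a Day 85 visit to be recorded as the Day 197 visit, which the Table 1 column does not allow, and item D would still catch the three listed reasons.
- **That Protocol 13.10 ("Participation of a subject will be discontinued in the event that") contradicts item D ("Meeting study withdrawal criteria (Protocol Section 13.10").** Ending participation also ends drug, so the two can stand together, and 14.2 only encourages staying where possible.

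**Conclusion.** The concern holds as a conflict between anchors that needs reconciling. If the last dose governs, a stop after any of doses 1 to 4 leaves no diary day in the DSQ endpoint window. The gap is 98 days after dose 1 and shrinks to 14 after dose 4; after dose 5 the window is fully covered. The biopsy is early by 140 days after dose 1, falling to 28 after dose 5.

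The effect on the planned primary analyses is limited to subjects who stay on study after a stop that item D does not clearly count as an ICE. That group may be small, and its size cannot be derived from the documents. No sample-size figure changes. The conclusion assumes nominal visit days and that some sites would count from the last dose, which the text permits but does not require.

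**What to change.** 1. Reconcile the synopsis (Study Design and Duration of Subject Participation), Protocol 5.1, 14.1 and 14.2, and SAP 4.2.5, so that one anchor governs subjects who stop drug and remain on study. The 8-week period after the last dose that applies to all subjects has to be part of that reconciliation, because a purely calendar schedule may name no visit for an early stopper until Day 169.
2. State in Protocol 14.2 that the daily DSQ continues through Week 24 (Day 168, counted from Day 1) for any subject still on study, whatever the date of the last dose.
3. Reconcile the passages on EGD timing for these subjects (Protocol 5.1, 14.2, Table 1 notes 14 and 32). No schedule is proposed here.
4. State in the SAP how an EGD outside the accepted Day 169 window is analysed. A window row in SAP 5.2 would not be enough: SAP 5.4.1 could carry the same early biopsy back in, and Protocol 8.1 and 10.4 let a rescue EGD replace the Day 169 one. The rule has to be consistent with both.

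The cost is a protocol clarification and a short SAP addition. The diary is completed at home, so item 2 needs no visit, only continued compliance checks by the site. Nothing here bears on when or why drug is stopped.

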15.1 General Considerations

This section outlines the nature and rationale for the statistical methods to be used for the analysis of the data from the study. A separate Statistical Analysis Plan (SAP), which will be documented as completed prior to unblinding the study, will describe data handling and statistical techniques in detail and will supersede the statistical methods described in the protocol. The SAP will detail any modifications to the analysis plan described below.

Unless specified otherwise, Baseline will be defined as the last observation before the first IV infusion of the study drug. All subject data will be listed for the double-blind placebo-controlled portion of the study. When appropriate, summary statistics of number of non-missing values, mean, median, standard deviation, minimum, and maximum will be computed for continuous variables, and summary statistics of number and proportion will be computed for categorical variables. Two-sided 95% confidence intervals will be provided for the mean and proportion. No formal statistical inferences will be made for safety parameters.

Unless otherwise specified, safety data will be summarized for each treatment group as well as for the 2 active dose groups combined.

Statistical analysis will be performed upon completion of the double-blind, placebo-controlled portion of the study. On completion of the OLE period, additional statistical analyses will be performed on data collected in that period and for the entirety of the study.

